One treatment modality that has solid evidence to treat both sensory nerve dysfunction and pain is low-level laser therapy (LLLT). LLLT has been established as viable therapy that modulates the body's own healing potential in recovery from injury and surgery. The proposed mechanism of LLLT is that low intensity laser light applied to body tissues penetrates and scatters into the tissue, and the scattered energy stimulates a cascade reaction that leads to upregulating of healing and a reduction of inflammation (8).

Existing studies have shown that LLLT can modulate the post-surgical healing and pain (9, 10) and nerve recovery in orthognathic surgery patients (11-15.). Two systematic reviews have also determined that LLLT is an efficacious therapy to reduce pain and have significant long-term improvement neurosensory deficits over placebo (16, 17). Additionally, the literature has a consensus that the adverse effects of LLLT are virtually non-existent, with both review papers noting no negative complications reported in any of the papers included in the reviews. Both review papers, however, discuss that the existing literature has too few studies that are well-designed. Both review articles recommended more objective analysis of neurosensory function, as many relied on objective patient reports, and a longer follow-up period. Additionally, many studies have been conducted using a split-mouth design, in which one side receives LLLT and the other side doesn't, in order to increase the sample size without increasing the number of patients. The issue is, according to the current understanding of LLLT (8, 9), the photobiomodulation effect can travel away from the site of LLLT administration. There are no documented adverse effects of LLLT.

This study would aim to study the effects of LLLT on pain, swelling and neurosensory function on patients who have undergone orthognathic surgery with BSSO and compare the effects on a control group of patients undergoing similar surgery who will not receive any extraordinary post-op care.

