### **Study Design**

The study will have two groups into which patients will be assigned to a control group and an experimental group through a random number generator. Patients will undergo their planned surgical procedure and receive instructions as per standard clinic protocols, in both pre- and post-operative settings. The standard instructions include information on pain and swelling management. The patients will also receive post-operative medications, including an NSAID and an opioid for pain management and a steroid to reduce inflammation and swelling. The patients will be seen at one-week intervals for six weeks for post-operative follow-ups, as per standard clinic protocols. The experimental group will undergo low level laser therapy (LLLT) at weekly intervals. Subject treatment assignments will remain blinded until the final subject has completed follow up and all data has been recorded and validated. Urgent, immediate unblinding due to medical emergency may be authorized by the Investigator. When possible, the treatment assignment will be provided to the treating physician in order to maintain the blind for the Investigator and study staff. All instances of subject unblinding will be documented in the study record.

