### Participant Recruitment

The patient pool for this study will be drawn from regular patients scheduled to undergo orthognathic surgery at Jacobi Medical Center. Patients who have been cleared for orthognathic surgery already must be in good health and understand the risks of the surgery. The only additional requirements for inclusion are 1) the planned surgery includes bilateral sagittal split osteotomies; 2) patients must be free from pre-operative inferior alveolar neurosensory deficiencies; 3) the patient cannot have an intra-operative

accidental fracture or rupture of the inferior alveolar nerve. The details of the whole orthognathic surgery will be recorded (including maxillary procedure, genioplasty, and direction of positional change of the mandible) but will not alter eligibility for enrolment in the study.

Since 2013, over 30% of the patients treated for orthognathic surgery at Jacobi Medical Center are between the ages of 15 and 18, which is in line with orthognathic surgery in general. As such, the study aims to include these patients in the potential pool of subjects. Because of the significant portion of patients under the age of 18 in general, and their inclusion will allow for age to be examined as a related factor in how healing proceeds. Their inclusion will also allow for an adequate sample size.

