### **Data analysis**

The primary outcome, change in neurosensory deficit, is measured by the three clinical tests, TPD, soft-stimulus and hard-stimulus. For TPD, the difference between the LLLT group and placebo group at each time point will be compared using an independent t-test, with alpha set at .05. The soft- and hard-stimulus tests for each region will be analyzed at each time point with a chi-square test. VAS pain score and swelling index will be analyzed using independent t-tests for the measurements on each side at each time point, with alpha set at .05. Linear regression will be performed to analyze the relationship of the pain, swelling and nerve tests with age, skeletal class, direction and magnitude of mandibular movement, and inclusion of genioplasty.

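### The maxillary procedure is recorded and free to vary, but the analysis plan leaves it out of the regression factors and of the pain and swelling comparisons

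*Combined protocol and SAP*

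**What the plan says.** Participant Recruitment requires that the planned operation include bilateral sagittal split osteotomies but leaves other surgery open. Its parenthesis on recorded operative details reads "including maxillary procedure, genioplasty, and direction of positional change of the mandible) but will not alter eligibility for enrolment in the study". The sample will therefore mix patients having mandibular surgery alone with patients who also have a maxillary procedure, and the data set will show which is which.

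The Data analysis section plans a linear regression of pain, swelling and nerve tests, examining their relationship "with age, skeletal class, direction and magnitude of mandibular movement, and inclusion of genioplasty". Of the three operative details named at recruitment, two appear in this list and the maxillary procedure does not. Treatment arm is not listed either.

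For the arm comparisons, the same section states: "VAS pain score and swelling index will be analyzed using independent t-tests for the measurements on each side at each time point". No covariate enters these tests. Under Study Design, patients are "assigned to a control group and an experimental group through a random number generator"; no stratification or blocking is described. No section explains why the maxillary procedure is left out.

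**The concern.** Operating on a second jaw could plausibly add to early pain and swelling. It may also be chosen to correct the same deformity that skeletal class and mandibular movement describe. Two consequences follow, and they differ in kind.

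- **Regression.** Randomisation does not protect comparisons between skeletal classes or directions of movement. If the procedure is commoner in one class or movement group once the other listed factors are held fixed, those coefficients can take up part of its effect.
- **Arm comparison.** Randomisation removes any systematic link between the procedure and the arm. What remains is chance imbalance that the t-tests do not adjust for, and outcome variation left in the error term although the variable explaining it has been collected.

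**Working it through.** **Inputs from the documents.** 23 patients per arm, 46 in total; difference 0.5, SD 0.5, so a standardised difference of 1.0; power 90% (Sample Size). Tests are run "with alpha set at .05" (Data analysis); sidedness is not stated and two-sided is assumed.

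**Inputs assumed.** Share with a maxillary procedure p = 0.3 to 0.5. Effect of the procedure on the outcome b = 0.5 to 1.0 within-stratum SD. The documents give neither.

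**1. The plan's own figure.** The normal approximation gives 2 × (1.960 + 1.282)² / 1.0² = 21.0 per arm. The noncentral t calculation gives 22.02, rounded up to 23, which matches the stated result of just over 22. Power at 23 per arm is 91.2%. A one-sided test would give 17.8 and does not match. The sample size is not in dispute. It was built on nerve-function studies and serves here only as a yardstick for pain and swelling.

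**2. Chance imbalance between arms.** With 23 per arm, the SD of the difference in shares is √(2p(1−p)/23).

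| p | SD of difference | P(15 points or more) | P(20 points or more) |
|---|---|---|---|
| 0.3 | 0.135 | 0.259 | 0.146 |
| 0.5 | 0.147 | 0.302 | 0.184 |

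If arm sizes are also left to chance, the 15-point probabilities become about 0.27 and 0.32. The range is thus 26% to 32%.

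A 15-point imbalance moves the arm difference by 0.15 × b = 0.075 to 0.15 SD. The standard error of the difference is √(2/23) = 0.295 SD, so the move is about a quarter to a half of one standard error.

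**3. Precision.** Omitting the factor multiplies the outcome variance by 1 + p(1−p)b². Power below is for 23 per arm and a true difference of 1.0 within-stratum SD.

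| p | b | Variance factor | Power, unadjusted |
|---|---|---|---|
| 0.3 | 0.5 | 1.052 | 89.8% |
| 0.3 | 1.0 | 1.210 | 85.4% |
| 0.5 | 0.5 | 1.062 | 89.6% |
| 0.5 | 1.0 | 1.250 | 84.3% |

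With adjustment, power is about 91%, ignoring the one degree of freedom used. Holding 90% unadjusted at p = 0.5 would take 24 per arm (b = 0.5) to 28 per arm (b = 1.0).

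**4. Regression.** The shift in the skeletal-class coefficient is b × δ. Here δ is the difference between classes in the share having the procedure, **given the other factors in the model**. The documents give no value for δ, so these are illustrations:

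- δ = 0: shift 0
- δ = 0.2: shift 0.1 to 0.2 SD
- δ = 0.4: shift 0.2 to 0.4 SD

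**5. Cost in degrees of freedom.** Counting one per factor, the regression's residual falls from 46 − 1 − 5 = 40 to 46 − 1 − 6 = 39. The arm comparison falls from 46 − 2 = 44 to 46 − 3 = 43.

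**The case against.** A reader might infer that the omission biases the laser effect on pain and swelling. It does not. Allocation is random, so the procedure has no systematic relation to arm, and the t-test's standard error already allows for chance imbalance. A shift can occur in a given trial, but that is not bias.

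A reader might also take confounding with skeletal class or movement as established, and put a size on it by multiplying an assumed effect by a crude difference in share between classes. The documents report no such association. A crude difference is also the wrong input, because direction and magnitude of movement are already in the planned model; the conditional difference could be smaller, larger or nil. Background and Significance describes correction in a Class II or Class III direction, so class and direction may overlap heavily. A separate class coefficient would then be hard to interpret with or without the maxillary term.

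Nor does the aim in Background and Significance to "compare the effects on a control group of patients undergoing similar surgery" promise adjustment. Two arms randomised from one pool of eligible patients satisfy it.

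Three further limits stand. Pain is rated on each side of the mandible and swelling is taped from chin to ear lobe, so a maxillary operation may affect them less than it affects the face as a whole. Pain and swelling are secondary outcomes. The t-tests omit every covariate, so the arm-comparison part is not peculiar to this one.

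These points limit the consequence. They do not explain why one of three named operative details was dropped.

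**Conclusion.** The point holds as a minor improvement. The procedure is recorded, free to vary and missing from both analyses without a stated reason.

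For the regression, distortion of the class and movement coefficients is possible but of unknown size, and it is zero if the procedure's frequency does not differ by class or movement given the other factors. For the arm comparisons of pain and swelling there is no systematic bias. The cost is unadjusted chance imbalance of 15 points or more in about 26% to 32% of trials, and power of about 84% to 90% instead of 91%. Those figures rest on an assumed share of 30% to 50%, an assumed effect of 0.5 to 1.0 SD, and the plan's standardised difference of 1.0 borrowed from the nerve-function outcome.

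**What to change.** In Data analysis:

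1. Add maxillary procedure (yes/no) to the listed regression factors.
2. For the pain and swelling arm comparisons, replace the unadjusted t-tests with a pre-specified linear model containing treatment and maxillary procedure, for the same sides and time points.

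The variable is already collected and is settled at surgery, before the first laser session, so treatment cannot influence it. The change needs no new patients, visits or measurements. It costs about one degree of freedom per model and slightly more analysis work, since the second step replaces a test with a model. It should be written in before unblinding so that it is not a post hoc choice.

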### **Safety monitoring**

While low-level laser therapy has no known adverse effects, safety monitoring of the study participants will be conducted in conjunction with their normal post-operative care during the duration of their participation, which occurs at each post-surgical visit. As orthognathic post-op care is generally overseen by the Jacobi Director of Oral & Maxillofacial Surgery (OMFS), the director will serve as the safety monitor. Adverse events during post-op care are reported to the Director of OMFS and documented into the patient chart. Any patient reporting an adverse event that is deemed, by the Director of OMFS, as clinically significant, will be withdrawn from the study and provided with all appropriate treatment. If more than one patient is withdrawn from the study through this mechanism, the study will be halted.

The Director of OMFS will report to the PI any adverse events requiring removal of a patient from the study, and the PI will document the adverse effects and provide a report to the IRB.

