### **Sample Size**

Published data (13-15) examining the effect of LLLT on IAN functional recovery shows a range of improvement versus placebo. The percentage of recovery shows that the LLLT treatment led to 27.3% (n=30, not split mouth, standard deviation not reported) (13), 13% (n=12, split mouth,  $7.4167 \pm 1.62$  vs  $8.5000 \pm 1.56$ ) (14), and 15% (n= 15,  $5.12 \pm 0.59$  vs  $5.97 \pm 0.45$ ) (15) improvement in sensory function, with . Additionally, one non-placebo controlled study of patients with long-standing documented neurosensory alteration following dental surgery (12) showed 33% improvement over baseline (n=4).

Using these studies, a sample size graph (Figure 1) was plotted in R Stats Package with the effect size versus sample size, with the standard deviation set to 0.5 and power set to 0.9. In order to detect an effect size of 0.5 with a SD of 0.5 at 90% power a sample size of just over 22 is needed. Therefore, 23 subjects per arm is required.

[figure not shown]

Figure 1- Effect size vs. Sample size.

The oral surgery clinic at Jacobi Medical Center treats approximately 50 patients with orthognathic surgery of the mandible annually, and has done so routinely for the last decade. Recruiting 46 patients to participate, even accounting for potential drop outs or failure to follow-up, should prove feasible.

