### Risk/Benefit

There are no known risks to low-level laser therapy.

The potential benefits to the patients are improved course of healing after orthognathic surgery.

Data will be stored on Jacobi shared servers using password-protected spreadsheets, that use codes to de-identify patients' names. The list of patient names that correspond to codes will be saved separately in a password-protected spreadsheet, and only the PI will have access the password.

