### **Informed Consent**

Patients who express interest in volunteering for the study will have the risks and benefits of the study explained to them, as well as that they may be assigned to either a control or experimental group. The details of study participation will be explained, including that the patients will not have any aspect of their surgery or post-care altered, other than LLLT treatment. It will be explained that the time commitment of the study is the same as the normal post-op care, with the exception of two additional visits at 8 weeks and 20 weeks post-op. It will be explained that patients may decide to not volunteer and their treatment will not be affected. Likewise, if the patients decide to drop out of the study, their treatment will not be affected. Information security will also be discussed with the patient during the consent process. All information in the discussion will be provided to the patient in written form, with a copy for them to keep. Patients who desire an alternate language will be offered translation services.

Patients over 18, will be given an informed consent form to sign. Patients who are under 18 will be asked to sign the informed consent form, to indicate their assent, while a legal guardian, who will also be present for the discussion of the risks and benefits of the study, will be asked to sign for consent.

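### Adverse events below the removal threshold stay in the patient chart: no step brings them into the study data or compares them by arm

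*Combined protocol and SAP*

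**What the plan says.** The Safety monitoring section describes two routes for adverse events.

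- **All events:** "Adverse events during post-op care are reported to the Director of OMFS and documented into the patient chart".
- **Events leading to removal:** "The Director of OMFS will report to the PI any adverse events requiring removal of a patient from the study". For these, "the PI will document the adverse effects and provide a report to the IRB".

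Removal depends on the Director's judgement: "Any patient reporting an adverse event that is deemed, by the Director of OMFS, as clinically significant, will be withdrawn from the study". The rule has no causality criterion and takes no account of arm. The section then adds: "If more than one patient is withdrawn from the study through this mechanism, the study will be halted".

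The Data analysis section covers two-point discrimination, the soft- and hard-stimulus tests, VAS pain, the swelling index and a set of regressions. It contains no analysis or table of adverse events. The documents describe no adverse-event form, no grading or attribution of events, and no transfer from the chart to the coded spreadsheets mentioned under Risk/Benefit.

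Risk/Benefit states: "There are no known risks to low-level laser therapy". Background and Significance makes a similar claim, but also reports that two systematic reviews found too few well-designed studies.

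**The concern.** A randomised trial with a dummy-treated control group and a blinded assessor is well placed to compare minor harms between arms. As written, the plan would not produce that comparison. An event judged not clinically significant is noted in the chart and goes no further. The events that do reach the PI come from very few patients, because the second removal halts the study.

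Two things are at stake. First, a report from a completed trial could say little about harms beyond the efficacy measures, and a near-empty adverse-event record could be misread as evidence of safety. Second, the PI and IRB have no stated route for seeing a pattern of lesser events, although the Director, who receives all events, could notice one.

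**Working it through.** **Inputs.** There are 23 patients per arm and 46 in total (Sample Size). The study halts when more than one patient is withdrawn for an adverse event, and only removal-level events go to the PI (Safety monitoring). The documents give no adverse-event rate, so every rate below is an assumption.

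**1. The plan's own denominator.** With a difference of 0.5, SD 0.5, 90% power and alpha 0.05 (two-sided assumed), the normal approximation is n = 2 × (1.960 + 1.282)² × 0.5² / 0.5² ≈ 21.0, rounded up to 22 per arm. The t-test version gives 22.02, matching the plan's figure of just over 22, and rounds up to 23 (power 91.2%). A one-sided test gives 18 and does not match. The figure of 23 per arm is reproduced and serves here only as a denominator.

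**2. The cap on the PI's record.** More than one withdrawal halts the study, so a trial that is never halted has 0 or 1 withdrawn patients among 46. The most extreme split is 1/23 v 0/23, with Fisher exact p = 1.0. The two-sided 95% Clopper-Pearson upper limits are 21.9% for 1/23, 14.8% for 0/23 and 11.5% for 1/46. These limits concern removal-level events only and say nothing about lesser ones.

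**3. What the halt would reveal.** Take removals to be independent, with none in control and probability p in each of 23 laser patients. Then P(halt) = 1 − (1 − p)²³ − 23p(1 − p)²².

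| Assumed removal rate | P(halt) |
|---|---|
| 0% control, 10% laser | 68% |
| 0% control, 20% laser | 96% |
| 5% in both arms (46 patients) | 68% |

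Substantial serious harm would therefore usually stop the trial. The third row shows that the same halt probability arises with no difference between arms, so a halt alone is not a comparison of harms.

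**4. What full collection would allow.** With 23 laser patients, the chance of at least one event is 1 − 0.95²³ = 69.3% at a true rate of 5%, and 1 − 0.90²³ = 91.1% at 10%. Zero events would give a one-sided 95% upper bound of 1 − 0.05^(1/23) = 12.2%. If 10% to 30% of patients had some event, that would be 46 × 0.10 = 4.6 to 46 × 0.30 = 13.8, or about 5 to 14 patients known only from charts.

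**The case against.** Several points on the other side stand and limit the finding.

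- A reader might infer that a completed trial can report at most one adverse event whatever the laser does. The documents do not support that. The rule counts withdrawn patients, and one patient may have several events. Serious harm would tend to halt the trial, which is itself a signal. Halting is also not defined as permanent.
- A reader might infer that no harm can be compared between arms. Nerve function is the primary outcome and pain and swelling are secondary. All are measured by a blinded assessor at each laser visit and compared by arm, so worsening in any of them could show there.
- A reader might infer that lesser events are lost. They are recorded in the chart, and nothing forbids abstracting them. What is missing is a plan to do so. Unplanned abstraction would depend on clinical notes not written to a common standard.
- A reader might doubt that monitoring reaches weeks 8 and 20, because Informed Consent describes the time commitment as that of normal care "with the exception of two additional visits at 8 weeks and 20 weeks post-op". But Safety monitoring ties the monitoring to the whole of a patient's participation, which includes those visits.

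It can also be said that safety is neither a hypothesis nor an outcome here, and that 23 per arm is small for harms. Both are true. They argue for a descriptive table rather than a test, and do not justify leaving the events out of the study data.

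**Conclusion.** The point holds for adverse events below the removal threshold that the efficacy measures do not capture, such as skin reactions at the laser sites, infection or delayed healing. Followed as written, the plan yields no by-arm data on these. In a trial that is never halted, the PI's record holds adverse events from at most one of 46 patients, so it could not support a statement on harms other than nerve function, pain and swelling.

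The cap follows from the text alone. The halt probabilities, detection chances and count of 5 to 14 patients rest on assumed rates and independence between patients. The 12.2% bound requires complete collection and zero events in all 23 laser patients. This gap does not undermine the efficacy analysis, but it is cheap to close and should be closed.

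**What to change.** In Safety monitoring, change the routing of adverse-event information:

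1. At each scheduled visit (day 1, weeks 1 to 6, week 8 and week 20), ask one standard adverse-event question covering the time since the previous visit.
2. Enter every event in the coded study data with its date, its severity and a judgement of relation to the laser or dummy procedure made without knowledge of arm.
3. Send the full event list to the PI. Removal-level events remain the subset reported to the IRB.

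In Data analysis, add a descriptive table by randomised arm showing the number of patients with any event and with each event type.

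The withdrawal and halting rules are left unchanged. The change concerns only what is recorded and tabulated.

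**Cost.** No extra patients or visits are needed. The question would be asked at most 46 × 9 = 414 times, with a little staff time for recording and the relation judgement, plus one table. Even then, the small sample limits the conclusion: zero events on laser would still be compatible with a rate of up to 12.2%.
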